## **11.3 Trial Phase (Visits 2-6)**

The participants will be followed monthly (every 4 weeks, +/- 7 days) with interval follow up telephone calls. Questionnaires will be administered during the telephone calls. Throughout the trial, participants will be reminded that participation in the research study does not replace clinical care. Moderate and severe asthma exacerbations will be asked about on monthly questionnaires. If a participant reports 3 severe asthma exacerbations (so defined by ATS criteria as an event requiring 3 or more days of systemic steroid treatment for asthma or an ED visit/hospitalization during which a steroid was prescribed), the participant's managing asthma healthcare provider will be notified. Additionally, if a participant has more 3 consecutive ACT or CACT scores that are equal to or less than 19, which is the threshold concerning for asthma control, the participant's managing healthcare provider will be notified.

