### **10. ADVERSE EVENTS:**

#### **10.1 Adverse events**

The risk for adverse events related to the study intervention are minimal. An adverse event will be defined as an unexpected accident, experience, or outcome that is unexpected (in terms of nature, severity, or frequency), is related or possibly related to the subject's participation in the research, and places subjects or others at a greater harm (including physical, psychological, economic, or social harm) than was previously known or recognized. Such events will be recorded as per 45 CFR part 46. Unexpected adverse events of moderate severity will be reported to the IRB within 10 working days of the investigator learning of the event.

As asthma is a chronic lung disease with waxing and waning impairment and risk, asthma exacerbations (both severe & moderate) and loss of control are not unexpected. We will consider an increased severity or frequency of such events as adverse events, although these will not meet the definition required for reporting to IRB as these such events are not anticipated to be related or possibly related to the research.

Specific examples of these are below. While these will not require reporting to the IRB, they will be captured as adverse events and safety procedures will be implemented as below:

1. If a participant has more than 3 severe asthma exacerbations during the study
2. If a participant has 3 consecutive ACT or C-ACT scores  $\leq 19$ .
3. If a participant has an FEV1  $< 80\%$  at either V1 or V7

These events will be recorded, parent or guardian/participant will be notified of possible poorly controlled asthma and will be encouraged to follow up with managing asthma specialist. With parental permission, PI or RC will reach out to managing asthma specialist to alert to concerns.

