## **14. DATA SAFETY AND MONITORING:**

[name] will oversee this clinical study thru close contact with research coordinators and close monitoring of data. [name] will review recruitment, enrollment and study visit data.. Study procedures will be reviewed and monitored by PI. All deviations/violations will be reported as per IRB specifications.

The risks of this study are minimal.

Please refer to adverse event section regarding reporting to the IRB. As noted in prior section, children with asthma are expected to have asthma exacerbations and loss of control. Should such events be deemed to be outside frequency or severity, contact will be made with participant's parent/guardian and with permission, PI or RC will reach out to asthma managing specialist to alert to potential concerns. Participants/families will be reminded at each visit that participation in this study does not replace clinical asthma care. All concerns about asthma control or management will be encouraged to be discussed with the participant's asthma care provider.

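### Sections 10.1 and 11.3 set different counts of severe exacerbations (more than 3 versus 3) for the same contact with the managing asthma clinician

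*Combined protocol and SAP*

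**What the plan says.** **Severe exacerbations.** Section 10.1 lists events for which "they will be captured as adverse events and safety procedures will be implemented as below". The first item reads "If a participant has more than 3 severe asthma exacerbations during the study". The procedures that follow are to record the event, tell the family that asthma may be poorly controlled, encourage follow-up with the specialist and, if the parent agrees, contact the specialist. Section 11.3 has its own rule, beginning "If a participant reports 3 severe asthma exacerbations", after which the managing provider is notified. Section 14 refers back to the adverse event section and states its condition without a number: "Should such events be deemed to be outside frequency or severity".

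**Asthma control scores.** Section 10.1: "If a participant has 3 consecutive ACT or C-ACT scores" at or below 19. Section 11.3: "if a participant has more 3 consecutive ACT or CACT scores that are equal to or less than 19".

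**Permission.** Section 10.1: "With parental permission, PI or RC will reach out to managing asthma specialist to alert to concerns". Section 14: "with permission, PI or RC will reach out to asthma managing specialist to alert to potential concerns". Section 11.3 attaches no such condition to its two provider notifications. Sections 11.2 and 11.4 require family permission to share spirometry or FeNO results, but state none for notifying the provider of an FEV1 below 80%.

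**The concern.** A count that triggers a safety action should be the same wherever the protocol states it. Here the two counts differ by one event and lead to the same contact, so they cannot be explained as thresholds for different purposes. At exactly 3 events, section 11.3 judges that the child's clinician should know, while the count in 10.1 has not been reached.

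What is at stake is consistent handling of children with frequent severe exacerbations: when the clinician is told, whether an adverse event is entered, and whether the parent gets the notice and advice in 10.1. Section 11.5 lists failure to follow the safety monitoring plan as a protocol violation, so coordinators need a single count to work to. The unclear score rule and the uneven permission wording concern the same procedures and are best tidied in the same edit.

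**Working it through.** The plan states no figure to reproduce. The check compares the sections and then sizes the group affected.

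**1. Severe-exacerbation count**
- 10.1: more than 3, so the stated count is met at the 4th event.
- 11.3: 3, so it is met at the 3rd event.
- Difference: 4 − 3 = 1 event.
- 14: no count, and it points back to the adverse event section. No section sets an order of precedence.

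For a child with exactly 3 events:
- Both sections applied: 11.3 is met and the clinician is alerted. The stated count in 10.1 is not met, so the adverse event entry and the 10.1 parent notice depend on how staff read 10.1.
- 10.1 alone: on its stated count, no alert until a 4th event.
- 11.3 alone: the clinician is alerted, but 11.3 does not mention adverse event capture or parent notice.

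**2. How many children have exactly 3**

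Inputs: 40 children (section 2.1, Aim 1) and 24 weeks of follow-up (Table 2). The mean number of severe events per child, m, is an assumption, taken over 0.25 to 1.0.

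Poisson: expected children = 40 × e^(−m) × m³ / 6.
- m = 0.25: 40 × 0.7788 × 0.015625 / 6 = 0.08
- m = 0.50: 0.51
- m = 0.75: 1.33
- m = 1.0: 40 × 0.3679 / 6 = 2.45

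With variation between children (negative binomial, variance m + m²): expected children = 40 × [1/(1+m)] × [m/(1+m)]³.
- m = 0.25: 40 × 0.8 × 0.2³ = 0.26
- m = 0.50: 0.99
- m = 0.75: 1.80
- m = 1.0: 40 × 0.5⁴ = 2.50

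Across both models the range is about 0.1 to 2.5 of 40.

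**3. Asthma control scores**

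A word has dropped out of 11.3. Read as '3 or more', the rule agrees with 10.1. Read as 'more than 3', it needs one further low score. If staff also apply 10.1, they act at 3 on either reading.

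**4. Permission**
- Required for contact with the clinician: 10.1 (all three listed triggers, including FEV1 below 80%) and 14 (exacerbations and loss of control).
- Not stated: 11.3 (exacerbations and scores), and 11.2 and 11.4 (FEV1 notification).
- Required for sharing results: 11.2 and 11.4.

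**The case against.** The strongest reply is that no alert need be lost. The two counts can be applied together, and staff who do so act at 3. Section 10.1 also introduces its list as examples of a wider rule that treats increased frequency or severity as an adverse event. A reader might infer that a child with exactly 3 goes unrecorded, or is never recorded. The documents do not support that: an illustrative list does not bar capture at 3, and the exacerbations are collected monthly as an outcome in any case. This part of the reply stands. What survives is narrower: the example's own count leaves that child out, so capture at 3 is uncertain.

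Other cover also counts. Section 14 provides for parent contact without a fixed number. The parent completes the questionnaire that reports the exacerbations. Section 10.2 urges contact with the specialist after a serious event such as a hospitalisation if the child has not yet been seen. These limit the harm but do not say which count governs.

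Two further readings are tempting. One is that the score wording in 11.3 causes children to be missed or alerted late. That requires both the reading 'more than 3' and staff who ignore 10.1, so it gives no usable size. The other is that, for a family that refuses permission, 11.3 and 14 cannot both be followed. Section 11.3 does not say that permission is unnecessary, and the consent form is not among the documents reviewed, so permission may already be given at enrolment. The difference in wording is real, but it supports only a harmonising edit.

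**Conclusion.** The inconsistency in the severe-exacerbation trigger is established from the text and does not depend on interpretation: one section states 3, another more than 3, for the same contact, and nothing settles it. The consequence is limited. With both sections applied, the clinician is alerted at 3, and the adverse event entry, parent notice and follow-up advice in 10.1 are left unclear for a child with exactly 3. With 10.1 alone, the alert comes one event late.

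The size, about 0.1 to 2.5 of 40 children, rests wholly on the assumed mean of 0.25 to 1.0 severe events per child in 24 weeks and on the two count models. No number is claimed for the score wording or for permission. Nothing here bears on sample size, power or the outcome analysis. Severity: minor.

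**What to change.** Main change: in 10.1, set the first listed trigger at '3 or more' severe exacerbations, so that it agrees with 11.3.

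Accompanying wording corrections:
- In 11.3, write '3 or more' consecutive ACT/C-ACT scores at or below 19, to match 10.1.
- In 11.2, 11.3 and 11.4, add 'with parental permission' to the provider-notification sentences, to match 10.1 and 14. This is not needed if consent at enrolment already covers such contact; in that case, say so.

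The cost is a few words in four sections, with no new visit, procedure or system. On the assumed rates, adverse event capture and the 10.1 parent notice become definite for about 0 to 3 children. Section 10.1 does not require these events to be reported to the IRB, so the added work is small.

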## **11.4 Exit visit (Visit 7)**

Visit 7 will be conducted in person. Eligibility for lung function tests and/or NEC will be assessed prior to study procedures. Questionnaires will be administered, height and weight will be obtained, lung function tests will be obtained (if eligible), and specimens will be collected (if applicable).

If a participant's spirometry demonstrates an FEV1 <80%, the family and participant's managing asthma healthcare provider will be notified. Per family permission, spirometry will be shared with managing asthma healthcare provider. If a participant's FeNO is above 20ppb, with family permission, FeNO will be shared with managing asthma healthcare provider.

## **11.5 Protocol Violations**

Protocol violations are defined as departures from accepted clinical research practices, study protocol, and/or study procedures that pose a risk to participant safety, adversely affect data quality and the integrity of the major scientific goals of the study, and/or involve a significant and repeated breach of participants' privacy. Protocol violations include (but are not limited to):

- Failure to obtain informed consent appropriately
- Enrollment and/or randomization of ineligible participants
- Incorrect intervention provided to participant
- Failure to follow the protocol safety monitoring plan
- Breaches of confidentiality resulting from lost, misplaced, or stolen study documents.

By the nature of their definition protocol violations are considered the most serious class of departure from the study protocol.

## **11.6 Protocol Deviations**

Protocol deviations are defined as departures from a study protocol or methods of a procedure that do not pose a risk to subject safety, do not adversely affect the integrity of the major scientific goals of the study, and do not involve a significant and repeated breach of participant privacy. Protocol deviations include (but are not limited to):

- Mistimed procedures
- Omission of protocol and/or procedure elements that do not impact participant safety
- Failure to carry out study procedures in the appropriate order, when applicable
- Submission or an outdated version of a data collection form

All protocol violations and deviations will be reported at the time of discovery to the PI. PD reports will be reviewed at regular meetings, no less than monthly.

## **12. SPECIMEN HANDLING**

If applicable, NEC and urine will be obtained at Visit 1 and 7. NEC will be processed and stored in the laboratory of [REDACTED] located in Rangos Research Building. Urine will be stored and processed in the laboratory of [REDACTED].

## **13. DATA MANAGEMENT**

### **13.1 Electronic Data Entry**

Research coordinators will endeavor to enter all information into redcap at time of visits. If paper forms are used, they will not contain personal identifiers and should be entered immediately into redcap as soon as possible.

### **13.2 Data Quality**

All data should be entered into Redcap. Questions will be labeled as required as to trigger an alert to the research coordinator upon saving if there are missing questions. Participants may choose not to answer any question.

### **13.3 Privacy and Data Security**

Procedures will be implemented to maintain the security and confidentiality of participant data, including assigning unique study identifiers rather than using names or other identifying information.

Participant records will be kept in accordance with IRB-approved consent procedures, and thereafter destroyed leaving available only de-identified data for use in publications, presentations, etc.

## **14. DATA SAFETY AND MONITORING:**

[name] will oversee this clinical study thru close contact with research coordinators and close monitoring of data. [name] will review recruitment, enrollment and study visit data.. Study procedures will be reviewed and monitored by PI. All deviations/violations will be reported as per IRB specifications.

The risks of this study are minimal.

Please refer to adverse event section regarding reporting to the IRB. As noted in prior section, children with asthma are expected to have asthma exacerbations and loss of control. Should such events be deemed to be outside frequency or severity, contact will be made with participant's parent/guardian and with permission, PI or RC will reach out to asthma managing specialist to alert to potential concerns. Participants/families will be reminded at each visit that participation in this study does not replace clinical asthma care. All concerns about asthma control or management will be encouraged to be discussed with the participant's asthma care provider.

## STATISTICAL PLAN:

Statistical Analysis: Data will be analyzed using SAS (SAS 9.4, Cary, N.C.). Baseline statistics per treatment group will be obtained. Bivariate analysis of covariates (age, sex, race/ethnicity, asthma severity, phenotype (i.e. atopic), socioeconomic status (SES), exposure to primary or secondary tobacco smoke, FeNO, use of controller medication, etc) between groups will be conducted using student t-test or Wilcoxon rank sum and Fisher's exact or Chi-square (where appropriate and based on distribution). Variables with significant differences between groups ( $P<0.05$ ) will be considered for inclusion in multivariate model selection. The effects of physical activity on the outcomes will be compared between groups. Baseline knowledge and usage of AQI will be assessed. Adherence to AQI will also be assessed and compared between groups, with potential stratification by AQI usage. Additionally, differences in weight and BMI will be assessed to evaluate if adherence to AQI promotes sedentarism and leads to increased weight gain. We will evaluate our outcomes (Aims 2 and 3) in three ways. First, we will evaluate the average difference (overall mean) between groups for our primary outcomes using T test or chi-square (where appropriate). Additionally, we will test the average mean difference between each treatment group by multivariate regression (linear for PAQLQ and ACT or CACT, and/or Poisson or logistic regression for mean asthma exacerbations depending on distribution) to allow for covariate adjustment. Second, we will use paired t-tests (or matched Wilcoxon signed-rank) to evaluate the within group effects (6 month mean – baseline) for each primary outcome. Third, to assess the effects over time in our intervention study (correlated repeat measures data), we anticipate analyzing our primary outcomes by generalized linear mixed models (GLMM). For these models, we will first evaluate the distribution of our primary outcome and determine the most appropriate link (e.g. for severe asthma exacerbations: logistic link if there are overall a high proportion of participants with none, or Poisson link if more consistent with count data). A stepwise approach will be used to build all multivariable models. All final models will include age, sex, race/ethnicity, SES, and tobacco smoke exposure. Additionally, the above outcomes will be stratified by age group (8-12y, 13-17y) to determine if the effects are greater in older children for whom the AQI recommendations may be better self-incorporated into outdoor physical activities, vs the younger group who will likely be more reliant on parental checking and activity modification.

Power calculations: Power calculations were conducted using G\*Power 354 and SAS (SAS 9.4, Cary, N.C.) using proc glmpower. For mean difference between treatment groups (routine vs. intervention) with sample size of 20 participants per group, two-tailed test, alpha 0.05, we will have  $\geq 90\%$  power to detect a mean difference of 1.05 between groups for mean asthma exacerbations, ACT and C-CACT, and PAQLQ. Our study will provide  $\geq 80\%$  power to detect a mean difference of 0.91. As the clinical difference for ACT is 2-3 points, we anticipate adequate power to detect a clinical difference. The estimated clinically meaningful difference in PAQLQ is 0.5, and our study may be underpowered to detect this small of difference with this analysis. For comparison within each treatment group, comparing the matched difference (end of study- baseline), using the same assumptions above, we will have  $\geq 90\%$  power to detect a mean difference of 0.76, and  $\geq 80\%$  power to detect a mean difference of 0.66. Therefore, we expect better ability to detect changes in PAQLQ within the groups than between them. For repeat measures, we estimated our power using proc glmpower using F test based on Hotelling-Lawley trace. We estimated a study allocation of 1:1, alpha 0.05, repeated measures at 1, 2, 3, 4, 5 months, lear correlation structure with base correlation 0.85 & decay rate of 1, with an estimated mean difference of 2, standard deviation of 2, which provides a  $\geq 90\%$  power for a treatment group size of 12 for overall mean and n=26 for time\*treatment.

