## 2. STUDY DESIGN:

Longitudinal (6 month) intervention trial, simple randomized 1:1 with stratification based on age (8-12 years, 13-17 years), non-blinded, to determine if adding the AQI to asthma action plans (AAP) reduces asthma exacerbations, and improves asthma control and quality of life (Figure 3).

Both groups will receive basic education about the AQI including what the AQI is, where to find it, how to use it, and behavioral recommendations by category. In our practice, discussion of the AQI varies by practitioner and patients. While true routine care is likely absence of discussion of the AQI, this was determined to be inappropriate for this study. First, consenting children to the study would result in some discussion of the AQI and therefore bias any true “routine care”. Second, we did not wish to withhold potentially vital asthma self-management to participants. Therefore, all children in the study will receive AQI

[figure not shown]
education. The routine group will receive written AAP only, and the intervention group will receive AAP + AQI written plan. Additionally, the intervention group will be required to download the app onto their or their parent's smartphone (available both for iPhone or android phones) **or** demonstrate the ability to navigate to the airnow.gov website to obtain the AQI at their location. Participants will be followed at monthly intervals for 6 months.

The goal of the AQI is to familiarize persons to their own sensitivities to air pollution and encourage self-modification as needed for personal symptom control. Additionally, there is a goal to prevent discouraging physical activity as most US persons do not meet current daily recommendations.

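### Covariates that are not forced into the models are taken forward only on a chance baseline difference at P<0.05, so asthma severity will usually go unadjusted; the cost is precision and a data-chosen model, not inflated error

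*Combined protocol and SAP*

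**What the plan says.** The first part of the Statistical Plan lists the baseline covariates to be compared between arms. After the demographic items come "asthma severity, phenotype (i.e. atopic), socioeconomic status (SES), exposure to primary or secondary tobacco smoke, FeNO, use of controller medication". Continuous items are compared by "student t-test or Wilcoxon rank sum", categorical ones by "Fisher's exact or Chi-square (where appropriate and based on distribution".

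The result decides what goes forward: covariates that differ between the arms at P<0.05 "will be considered for inclusion in multivariate model selection". Two further sentences complete the rule. One is "A stepwise approach will be used to build all multivariable models", with no entry or stay criteria. The other is "All final models will include age, sex, race/ethnicity, SES, and tobacco smoke exposure".

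Severity, phenotype, FeNO and controller use are therefore screened but not forced. The design does not balance them either: allocation is "simple randomized 1:1 with stratification based on age (8-12 years, 13-17 years", so age is the only stratification factor (section 2). Section 5.1 admits mild, moderate and severe persistent asthma, so severity will vary within the sample. Section 2.1, Aim 2, counts asthma severity among the recognised contributors to exacerbations.

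**The concern.** A covariate earns its place in a randomised comparison by predicting the outcome. A significance test of baseline balance does not measure that. It tests whether the arms come from the same population, which randomisation has already settled, so it passes each covariate at the size of the test whether or not the covariate is prognostic.

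Two things are at stake. A predictor worth adjusting for will usually be left out, in a trial of 40 children whose own power statement concedes it may be short of power for the PAQLQ. And the content of the adjusted model is settled by chance imbalances seen in the data, then by a stepwise procedure without stated criteria, so it cannot be known in advance.

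**Working it through.** **Inputs from the documents.** 20 per arm, two-sided alpha 0.05, detectable differences 1.05 and 0.91 (Power calculations); entry threshold P<0.05 (Statistical Plan). **Assumed:** SD = 1, because the plan states none for the two-group comparison, and outcome correlations r of 0.3, 0.5 and 0.7, because the documents give none.

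**1. The plan's own power.** Two-sample t-test with 38 df and noncentrality d × √(20/2). For d = 0.91 this is 0.91 × 3.162 = 2.878, power 80.1%. For d = 1.05, power is 89.9%. The stated 80% and 90% are thus reproduced, to rounding, with SD = 1.

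**2. How often a covariate passes.** Under randomisation the pass rate is the size of the screening test. At 20 against 20:

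| Covariate and test | Pass rate |
|---|---|
| Skewed continuous (as FeNO may be), t-test | 4.4% |
| Same, Wilcoxon | 5.0% |
| Three-level severity, chi-square | 4.8% |
| Binary, chi-square (prevalence 0.3 to 0.9, assumed) | 3.9–5.3% |
| Binary, Fisher (same prevalences) | 1.2–2.5% |

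Each covariate is left out in about 95% of trials or more. For all four together, 0.95⁴ = 81.5% if independent, or 82–84% at pairwise correlations of 0.3 to 0.5. At least one passes in 1 − 0.815 = 18.5% if independent.

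**3. The imbalance needed.** For a continuous covariate tested by t-test: t(0.975, 38) × √(2/20) = 2.024 × 0.316 = 0.64 SD. Smaller imbalances go unadjusted.

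**4. Precision lost.** One continuous covariate, linear outcome, no forced terms, difference 0.91 SD. Planned adjustment reduces the residual SD to √(1 − r²), so noncentrality is 0.91/√(1 − r²) × √10 × √(37/38), with 37 df:

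- r = 0.3: residual SD 0.954, noncentrality 2.98, power 82.6%
- r = 0.5: 0.866, 3.28, 89.1%
- r = 0.7: 0.714, 3.98, 97.2%

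Simulation with 20,000 trials per setting agrees, and adds the gated rule (adjust only if the covariate differs at P<0.05):

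| r | Power, gated | Power, always adjusted | Type I error, gated |
|---|---|---|---|
| 0.3 | 80.2% | 82.6% | 4.7% |
| 0.5 | 81.1% | 89.3% | 4.4% |
| 0.7 | 82.0% | 97.3% | 3.6% |

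**5. With forced terms.** The planned models carry five forced covariates. Taking these as seven degrees of freedom of pure noise (an assumption), power at r = 0.5 is about 71% gated and 80% always adjusted. The levels fall; the gap stays at about 9 points.

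**The case against.** Several points on the other side stand.

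- **The exclusion is inferred.** The plan says which variables will be considered; it does not say that others are barred, and the stepwise sentence is loose enough to hide another route. But none is described, and if one is intended the SAP has to state it.
- **Prognostic strength is documented only in part.** A reader might infer that all four covariates are strong predictors. Aim 2 supports a prognostic role for severity, and mentions allergic triggers, but gives no strength and refers only to exacerbations. FeNO and controller use get no such support. At r = 0.3 the gain is only 2 to 3 points of power.
- **The simulation is simpler than the planned models.** It has one covariate and a linear outcome. The levels do not carry over directly to the Poisson or logistic models for exacerbations, and any gain shrinks if severity is correlated with forced terms such as SES or smoke exposure.
- **The first planned analysis is untouched.** The unadjusted t-test or chi-square does not use the entry rule and is valid under randomisation.
- **It is a pilot.** True, but the plan tests efficacy hypotheses and claims 80–90% power, and chance imbalances are largest in small samples.

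A stronger reading is that the rule inflates false positives. In the roughly 15% of simulated trials with a non-significant imbalance above 0.4 SD, the unadjusted test rejects a true null in about 8–9% at r = 0.5 and about 11% at r = 0.7. That slice is selected on the imbalance. Over all trials the gated rule stays at or below 5%, so the inference of inflated error fails.

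**Conclusion.** The point holds as a fault of precision and pre-specification. The entry rule selects on chance imbalance, and the one covariate among the four that the protocol itself names as contributing to exacerbations, asthma severity, is neither stratified on nor forced. The 95% exclusion is per covariate and should not be read as all four together, for which the figure is about 81–84%.

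The size depends on a correlation that the documents do not supply: in the simplified setting, about 2 points of power at r = 0.3, 8 at 0.5 and 15 at 0.7, all at 0.91 SD with SD taken as 1. The structural point, that a covariate's entry is unrelated to its prognostic value, needs neither those correlations nor the SD.

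**What to change.** Delete the P<0.05 entry rule, and the stepwise step for these covariates. Show the baseline table descriptively. Name a small adjustment set in the SAP, chosen by prognosis:

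- for all outcomes, the age stratum and baseline asthma severity;
- for ACT/C-ACT and for PAQLQ, also the Visit 1 value of the same outcome;
- for exacerbations, also Visit 1 ACT/C-ACT.

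ACT/C-ACT and PAQLQ are already collected at Visit 1 (Table 1). Severity is an eligibility descriptor and a screened covariate but is not an item in Table 1, so the plan should say that it is recorded, and how it is graded, before randomisation.

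The cost is SAP wording and about two degrees of freedom: one for severity as an ordered score and one for the baseline measure (one more if severity is a three-level factor). With 40 children the model must stay small. The sponsor should therefore also decide now which of the five forced terms have a prognostic case, so that severity and the baseline value can take the place of weaker terms.
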